Within O&G, at Certificate of Completion of Training (CCT), there is concern that trainees lack the confidence and skills to perform the same breadth of procedures as the previous generation.³ An intra deanery survey showed that 67% of O&G trainees felt inadequately prepared for CCT⁸. In 2012, analysis of 155 successful applications for CCT in general surgery (GS) revealed that only 67% of the cohort had achieved the logbook requirement of 1600 cases and around 73% had the necessary experience in index procedures.⁹ There is currently no literature to highlight expectations and opinions of consultants or programme directors of trainees' skills within GS or O&G in the UK, which we believe to be one of the indicator of training standards.

Whilst the requirements for CCT for general operative skills in open and laparoscopic surgery are comparable in both specialties, the training pathways defer significantly. GS training is 8 years in duration (CT1, CT2, ST3-ST8), whereas O&G consists of 7 years of specialty training (ST1–ST7). The ST1-ST5 years in O&G is mainly devoted to obstetrics and only those trainees pursuing a gynaecological training pathway undertake an intensive period of surgical training in the last two years of their training. We believe there is also earlier exposure to laparoscopy in GS training with a greater volume of laparoscopic work in comparison to O&G training. To our knowledge, there is no direct comparison of O&G and GS training pathways and outcomes in laparoscopic skills.

It is known that greater exposure to laparoscopic training is associated with “muscle memory” and may contribute to reducing physical and mental stress of the surgeon. It is not known whether the existing training is sufficient to meet the demands of a laparoscopic gynaecological or GS consultant or whether the differences in training affects the development of fundamental laparoscopic skills (FLS). These FLS include spatial awareness, hand eye co-ordination, bimanual dexterity and laparoscopic suturing. We would expect trainees to be better at FLS with more laparoscopic surgery exposure. The measurement of muscular and cognitive

fatigue can be regarded as a surrogate marker of exposure to laparoscopy giving further insights into the quality of laparoscopic training between the two training programs.

Hypothesis

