**As OG training covers both obstetrics and gynaecology curriculums, we will recruit trainees in their final two years of training, with gynaecology special interest, who are undertaking at least one gynaecology Advanced Training Skills Modules (ATSM). These include advanced laparoscopic training, open and laparoscopic benign abdomen, urogynaecology, gynaecology-oncology and reproductive medicine. These ATSMs involve core laparoscopic skills such as laparoscopic suturing as an essential component of their curriculum.

Trainees (Exclusion Criteria)

Those trainees who have had substantial pre-training experience in laparoscopic surgery such as those who have completed another surgical speciality training, have worked as clinical fellows or speciality doctor with substantial exposure to laparoscopic work will be excluded. Those trainees who are currently out of program/training and not doing regular clinical work or those trainees outside the North West deanery will also be excluded. For the safety of others anybody with positive Covid-19 test, symptoms or contact with someone infected with the virus will be excluded.

Withdrawal

Participation in this study is voluntary and all participants will be required to provide explicit consent (**Appendix 3 &4**). Participants can withdraw at any time by contacting a member of the research team.

Study Protocol

Part 1 consists of questionnaires sent out to Consultants and trainees.

Consultant Questionnaire (Appendix 1)

A questionnaire will be sent to consultants nationally via the RCOG and BSGE (O&G consultants) and ASGBI (GS consultants) to get an idea of their own level of laparoscopic surgical experience and their expectations of laparoscopic competencies required at CCT by trainees. No personal details will be requested in the questionnaires.

The email accompanying the questionnaires email will contain a brief introduction to the study, a participant information sheet (**Appendix 3**) and consent form (**Appendix 4**) as attachments and a link to the online questionnaire. All questionnaires will be returned anonymously via survey monkey service.

Trainee Questionnaire (Appendix 2)

A short questionnaire will be sent to trainees nationally via the RCOG and BSGE assessing their perception of self rated laparoscopic ability and skills they rate as important at CCT. No personal details will be requested in the questionnaires.

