Appendix

- 1. Consultant Questionnaire (Appendix 1)**
- 2. Trainee Questionnaire I (Appendix 2)**
- 3. Participant information sheet (Appendix 3)**
- 4. Consent Form 1 (Appendix 4)**
- 5. Consent form 2 (Appendix 5)**
- 6. Trainee questionnaire II (Appendix 6)**
- 7. Trainee Standardised Task Instructions (Appendix 7)**
- 8. Validated Laparoscopic tasks scoring Form (Appendix 8)**
- 9. Validated suturing scoring system (Appendix 9)**
- 10. EMG will be measured by placing wireless electrodes over arms, neck and back muscles (Appendix 10)**
- 11. EEG will be recorded using wireless electrodes over parietal cortex using validated protocols. (Appendix 11)**
- 12. Equipment (Appendix 12)**
- 13. Assessor Instructions (Appendix 13)**

Appendix 1

Consultant Questionnaire: Expectations of Fundamental Laparoscopic Skills Required by the end of Higher Specialty Training

Gender

	Mark with 'X'		Mark with 'X'
Male		Female	

Please state the year you became a consultant.

Specialty

	Mark with 'X'		Mark with 'X'
General Surgery – Colorectal/HPB/Upper GI		Gynaecology only	
		Obstetrics and gynaecology	

Where did you complete the majority of your higher surgical Training?

	Mark with 'X'
UK	
EU, not UK	
Outside of the EU	

What percentage of your work do you perform laparoscopically?

	Mark with 'X'
0-25%	
25-50%	
50-75%	
75-100%	

What are your expectations of required laparoscopic abilities of trainees at CCT? For gynaecology consultants please base your answers on a trainee who is undertaking the following ATSM: Advanced laparoscopy, open and laparoscopic benign abdomen, gynae-oncology and other sub specialty trainees involving major laparoscopic work. Please mark your answer with an 'X'

Strongly Disagree – 1, Disagree -2, Neither agree nor disagree-3, Agree -4 and Strongly agree – 5.

Laparoscopic ability	1	2	3	4	5
Proficient in obtaining laparoscopic intra-abdominal access					
Proficient in recognition of anatomy and anatomic tissue planes laparoscopically					
Proficient in safe manipulation of tissue laparoscopically					
Proficient in dissection of tissue planes laparoscopically					

Able to control bleeding laparoscopically using diathermy/energy devices.					
Able to control bleeding laparoscopically using endovascular staplers/haemolocks/endoloops					
Able to control bleeding laparoscopically using haemostatic agents ie Flowseal/surgicel					
Proficient in appropriate use of laparoscopic energy devices					
Proficient in laparoscopic suturing					

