Male (including transgender men)		Female (including transgender women)	Other		Prefer not to say	

2. Specialty

	Mark with 'X'		Mark with 'X'
General Surgery – Colorectal/HPB/Upper GI		Other	
Obstetrics and gynaecology			

3. Are you currently enrolled in a specialty training program?

Yes/ No

4. Which deanery are you currently enrolled in a training program in? Please mark your answer with an X.

North East Yorkshire and Humber North west
 East midlands West midlands East of England South West
 Thames valley Wessex Kent/surrey/Sussex (KSS)
 North central and East London North West London
 South London.

5. Which level of training are you currently?

Please mark your answer with an X					
ST3	ST4	ST5	ST6	ST7	ST8

6. When did you commence higher surgical training/Obs and Gynae Training? (Year) _____

7. Please select the NHS deanery in which you are currently employed in. Please mark your answer with an X.

North East Yorkshire and Humber North west
 East midlands West midlands East of England South West
 Thames valley Wessex Kent/surrey/Sussex (KSS)
 North central and East London North West London
 South London. None of the above.

8. What are your **expectations** of required laparoscopic abilities of trainees at CCT? Please mark your answer with an 'X'

Strongly Disagree – 1, Disagree -2, Neither agree nor disagree-3, Agree -4 and Strongly agree – 5.

Laparoscopic ability	1	2	3	4	5
Proficient in obtaining laparoscopic intra-abdominal access					
Proficient in recognition of anatomy and anatomic tissue planes laparoscopically					
Proficient in safe manipulation of tissue laparoscopically					
Proficient in dissection of tissue planes laparoscopically					
Able to control bleeding laparoscopically using diathermy/energy devices.					
Able to control bleeding laparoscopically using endovascular staplers/haemolocks/endoloops					
Able to control bleeding laparoscopically using haemostatic agents ie Flowseal/surgicel					
Proficient in appropriate use of laparoscopic energy devices					
Proficient in laparoscopic suturing					
Proficient in use of laparoscopic staplers					

How would you rate **your own confidence** with the listed laparoscopic skills? Please mark your answer with an 'X'

Not at all confident -1, Not so confident-2, Somewhat confident -3, Very confident -4, extremely confident-5.

Laparoscopic ability	1	2	3	4	5
Proficient in obtaining laparoscopic intra-abdominal access					

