Proficient in recognition of anatomy and anatomic tissue planes laparoscopically					
Proficient in safe manipulation of tissue laparoscopically					
Proficient in dissection of tissue planes laparoscopically					
Able to control bleeding laparoscopically using diathermy/energy devices.					
Able to control bleeding laparoscopically using endovascular staplers/haemolocks/endoloops					

Able to control bleeding laparoscopically using haemostatic agents ie Flowseal/surgicel					
Proficient in appropriate use of laparoscopic energy devices					
Proficient in laparoscopic suturing					
Proficient in use of laparoscopic staplers					

Appendix 6

Trainee questionnaire II

ANONYMISED CODE HERE e.g LAP 01 G2

Name----- Age-----

Email----- contact phone number.....

--x-----x-----x-----x-----x-----x-----x-----x-----x-----x-----x-----

Your personal contact details will be stored separately and securely from the remaining questionnaire and scoring sheets.

ANONYMISED CODE HERE e.g LAP 01 G2

Gender-----Deanery.....Specialty-----Training grade/Job title -----

Start of ST3 training (Year)

Weight----- height----- BMI-----

Q1.Dominant handedness. Please tick one of the following 3 options.

I am right handed	I am left handed	I am bi-dexterous
-------------------	------------------	-------------------

Q2. Do you play video games on average? Please tick 'Yes/No' below. If answering 'Yes' please tick the appropriate frequency of use from the below list.

Yes	Daily	
	Weekly	
	Monthly	
	Every 3 months	
	Yearly or less frequently	
No- I don't play video games		

Q3.Do you use a laparoscopic simulator? Please tick 'Yes/No' below. If answering 'Yes' please tick the appropriate frequency of use from the below list.

YES	Daily	
	Weekly	
	Monthly	
	Every 3 months	
	Yearly or less frequently	
NO- I don't use lap simulator		

Q4. Please indicate the type and approximate number of laparoscopic courses have you attended during your current training program? If none attended, please indicate not applicable here.

Type of courses	Box trainer	Virtual reality	Cadaver based	Animal tissue	Other
No of courses attended					

Q5. Have you done laparoscopic work during 'time out of training' or before starting your current training program?

Yes	No
-----	----

If answering yes to Q4, how frequently were you doing operative laparoscopic work (on average) during this period?

>2 times per week.	2 times per week.	Once weekly.	Once fortnightly.	Once monthly.	Less than once monthly.

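### The Part 1 trainee form defines its specialty groups unequally: the general surgery box names three subspecialties, while all O&G trainees share one box with no ATSM or special-interest field

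*Protocol*

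**What the plan says.** The Part 1 trainee form (Protocol, Appendix 2) is an anonymous online survey sent to trainees nationally.

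- **Item 2, specialty.** The GS box reads "General Surgery – Colorectal/HPB/Upper GI". The O&G box reads "Obstetrics and gynaecology" and has no qualifier. The only remaining box is *Other*, with no space to specify. No item asks for a subspecialty, a gynaecology interest or an ATSM.
- **Item 5, grade.** "Which level of training are you currently" is answered on one scale, ST3 to ST8, for both specialties.
- **Item 6, start of training.** "When did you commence higher surgical training/Obs and Gynae Training? (Year" puts two starting points into one question.
- **Item 8, expectations.** The question is about trainees at CCT in general, with no restriction on the kind of trainee.

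Elsewhere the protocol narrows the O&G reference group:

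- In the consultant form (Appendix 1), the expectations and experience blocks both carry the instruction "For gynaecology consultants please base your answers on a trainee who is undertaking the following ATSM", followed by a list.
- In Part 2 (Study Population), the final-two-year O&G trainees must be those "with gynaecology special interest, who are undertaking at least one gynaecology Advanced Training Skills Modules (ATSM".

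The Part 2 trainee form (Appendix 6) asks everyone for "Start of ST3 training (Year".

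**The concern.** The protocol's own background explains why an unqualified O&G box is a problem. It describes the first five O&G years as mostly obstetric, and it reserves intensive surgical training for those on a gynaecological pathway in their last two years. A single O&G box therefore mixes trainees with very different laparoscopic exposure. The GS box, by its label, is confined to three fields.

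Two comparisons are affected:

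1. **GS against O&G trainees.** The label selects by subspecialty on one side and not on the other.
2. **O&G consultants against O&G trainees on what is expected at CCT.** The Hypothesis section predicts a discrepancy within each specialty. O&G consultants are told to picture an ATSM trainee. O&G trainees are not, and those on an ATSM cannot be picked out. Part of any discrepancy could come from the two sides having different trainees in mind.

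Item 6 matters less. If expectations or confidence were ever set against years since the start of training, the two specialties might not be counting from the same point.

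**Working it through.** **Item 2: how each instrument defines its groups**

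| Instrument | GS | O&G |
|---|---|---|
| Consultant form (Appendix 1) | Respondent box names the same three subspecialties | Answers refer to a trainee on listed ATSMs |
| Part 2, senior trainees (Study Population) | ST7/ST8, no subspecialty stated | ST6/ST7 with gynaecology interest and at least one gynaecology ATSM |
| Part 1 trainee form (Appendix 2) | Box names three subspecialties | One box, no ATSM or interest recorded |

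The Part 1 trainee form is the only one of the three that narrows GS and leaves O&G unrestricted. Within GS, the consultant and trainee boxes match. Within O&G, they do not.

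*Recoverability.* The Study Design section says that Part 1 surveys carry no personal details and come back anonymously. A GS trainee who ticks *Other* cannot be told apart from a trainee in another specialty, and an O&G trainee's ATSM status cannot be found out afterwards. Grade (item 5) identifies senior O&G trainees but not which of them are on a gynaecology ATSM.

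**Item 6: size of the difference in starting points**

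The pathways are given in the background section: "GS training is 8 years in duration (CT1, CT2, ST3-ST8), whereas O&G consists of 7 years of specialty training (ST1–ST7". Assume full-time, uninterrupted progression and count years since the starting point at the beginning of grade ST*g*.

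- O&G, counted from ST1: *g* − 1
- GS, if higher surgical training means ST3 onward: *g* − 3
- GS, if the respondent counts from CT1 (two years before ST3): *g* − 3 + 2 = *g* − 1

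| Grade | O&G | GS from ST3 | Difference | GS from CT1 | Difference |
|---|---|---|---|---|---|
| ST3 | 2 | 0 | 2 | 2 | 0 |
| ST5 | 4 | 2 | 2 | 4 | 0 |
| ST7 | 6 | 4 | 2 | 6 | 0 |

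At equal grade the difference is 2 years on the first reading and 0 on the second. Over the whole programme on the first reading, GS covers ST3 to ST8 (6 years) and O&G covers ST1 to ST7 (7 years), a difference of 1 year because GS runs one grade further.

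With the Appendix 6 item, both specialties count *g* − 3, so the difference at equal grade is (*g* − 3) − (*g* − 3) = 0.

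**The case against.** Much of the case on the other side stands.

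- **No stated analysis uses the item 6 year.** The protocol's training-stage variable is grade, and item 5 records it on a common scale. This reduces item 6 to a wording point.
- **The GS label is the same on the consultant form.** The within-GS comparison is therefore consistent, and the narrowing may be deliberate. The gap that remains is on the O&G side and between the specialties.
- **A GS-against-O&G contrast in trainee confidence is not a listed outcome.** Objective 3 and the questionnaire outcome both concern consultants' views. Trainee expectations enter through the Hypothesis section.
- **A GS trainee who is undeclared or in another field might still tick the only box headed general surgery.** How many would choose *Other* is not known.
- **Changing a live survey has a cost.** It leaves two classifications in one anonymous dataset.

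A reader might also infer four stronger things that the documents do not support.

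1. *That the labels widen a GS-O&G confidence gap.* Nothing gives the confidence of GS trainees outside the three fields, or the mix of respondents. The direction is unknown.
2. *That item 6 shifts the specialties by a fixed two years.* Higher surgical training is not defined. Appendix 1 uses the same phrase for consultants of both specialties, so it is not reserved for GS training after CT2.
3. *That Parts 1 and 2 contradict each other on the start date.* They are separate forms, taking part in one does not depend on the other, and no linkage is described.
4. *That item 5 adds to the asymmetry by starting at ST3.* Its options are identical for both specialties.

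**Conclusion.** The specialty item of the Part 1 trainee form defines its two groups unequally. It also leaves the O&G consultant-trainee comparison of expectations without matching reference groups. That follows from the text alone and needs no assumption about numbers. Because responses are anonymous, the missing information cannot be filled in later. The direction and size of any resulting bias cannot be determined from the protocol.

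Item 6 is a lesser flaw. The difference at equal grade is 0 to 2 years, and the upper figure assumes that higher surgical training means ST3 onward and that progression is full-time. Start year can be checked against grade for trainees with unbroken full-time training. It cannot be for the part-time trainees whom the protocol recognises in its grade footnote.

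Severity is minor. Part 1 serves a secondary outcome, and neither the primary task outcomes nor any stated figure changes.

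**What to change.** 1. **Item 2.** Offer General Surgery and Obstetrics and Gynaecology as whole specialties. Follow each with a field for subspecialty or ATSM that includes *not yet declared*. List the ATSMs one by one, because the consultant form and the Part 2 criteria do not name the same set, and separate entries allow either definition to be applied.
2. **O&G consultant-trainee comparison.** Base it on trainees whose ATSM matches the consultant form's list. Repeating the consultant form's instruction in item 8 for O&G respondents would also align the trainee whom both sides have in mind.
3. **Item 6.** Replace it with the Appendix 6 item on the start of ST3, for both specialties.
4. **Responses already received.** Flag them as collected on the old form, and use grade (item 5) as the training-stage variable.

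*Cost.* These are a few wording edits to an online form whose recruitment the Study timeline lists as ongoing from April 2021. Earlier responses keep the old categories, and any *Other* answers among them cannot be reclassified. Restricting the O&G comparison to matching ATSM trainees also makes that group smaller, by an amount the protocol does not allow one to estimate.

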The email accompanying the questionnaires will contain a brief introduction to the study, a participant information sheet (**Appendix 3**), consent form (**Appendix 4**) as attachments and a link to the online questionnaire.

The completed questionnaires will be returned to us via 'survey monkey' service.

Part 2:

This phase consist of four FLS tasks and EMG/EEG data recording on a randomly selected small subset of trainees.

The relevant trainees (ST3, ST4 , ST5 grades in both specialties, ST6/7 in O&G and ST7/8 in GS) will be identified and approached through north west deanery on our behalf who hold contact details for all trainees in the region. This email will contain a brief introduction to the study and request their help by volunteering with the FLS tasks if they meet the selection criteria. This email will contain a participant information sheet and consent form (Appendix 3 & 5 respectively) as attachments. Trainees will be able to self select from this information if they meet the inclusion criteria and volunteer their help. There will be a secure email address for them to reply to if they wish to volunteer. In addition to above recruitment methods we will consider the use of social media and direct emails to increase trainee recruitment for the study

Volunteering for FLS (part 2) is not contingent on trainees completing the questionnaire in part 1 of study. Trainees can help with both parts of the study or one or the other as they are able.

Trainees volunteering for the FLS tasks will be requested for their preferred contact number or email. This will be used by the research team to verify their inclusion criteria and offer a convenient date from a choice of 6 days over 3 separate weekends for the FLS tasks in part 2. By engaging in this process we are restricting our access to personal details on a strictly 'need to know basis', i.e. only dealing with personal details of trainees interested in volunteering for FLS tasks.

On the day, trainees will be asked to fill out a short questionnaire on demographic details, previous laparoscopic experience, physical fitness and presence of any musculoskeletal symptoms as these are potential confounding variables (**Appendix 6**). A written consent form will be completed at this stage (**Appendix 5**).

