--------------------	-------------------	--------------	-------------------	---------------	-------------------------

Q6. In which training grade were you **initially** allocated to an operative laparoscopy list?.....

Q7. How regularly are you allocated to a theatre list involving operative laparoscopy? Please tick one of the following statements.

>2 times per week.	2 times per week.	Once weekly.	Once fortnightly.	Once monthly.	Less than once monthly.
--------------------	-------------------	--------------	-------------------	---------------	-------------------------

Q8. When allocated to a theatre list involving operative laparoscopy, do you '**Generally**' get the opportunity to perform some or most of the operation in suitable training cases, or are you mostly assigned as an assistant or an observer? Please tick one of the following statements or free text your answer if you are able or want to provide more details.

I get the opportunity to perform some or most of the operation in cases suitable for training.	I am usually assigned to an assistant's role.	I usually observe the case only.	
--	---	----------------------------------	--

Space for free text answer.-----

Q9. How frequently were you involved in emergency operative laparoscopy such as lap appendicectomy, cholecystectomy, laparoscopic management bowel obstruction, of ectopic pregnancy and or ovarian torsion? Please tick one of the statements below.

>2 times per week.	2 times per week.	Once weekly.	Once fortnightly.	Once monthly.	Less than once monthly.
--------------------	-------------------	--------------	-------------------	---------------	-------------------------

Physical health and fitness:

What form of regular exercise do you undertake? E.g. Walking/running/resistance training/yoga etc

.....

How frequently do you undertake the above exercise in a week? Please choose by ticking the appropriate statement from the list below.

Activity level

Inactive (less than 30minutes a week)	
Moderately Active (Between 30 and 60 minutes a week)	
Active (Between 60 and 150 minutes a week)	

Musculoskeletal symptoms

During the past 12 months have you had any trouble (ache/pain/discomfort/numbness) in any of the following please: (please circle the appropriate response)

Body system	Yes	No
Neck		
Right shoulder		
Left shoulder		
Right wrist		
Left wrist		
Right upper back		
Left upper back		
Right lower back		
Left lower back		

Appendix 7

Trainee Instructions for laparoscopic tasks

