Participants will be fitted with wireless EMG sensors. The EMG data collection procedures will follow established protocols regarding site preparation and electrode placement, as well as data collection, processing and normalisation. Briefly, the site will be shaved and cleansed with alcohol wipes, with the bipolar electrodes placed on the belly of the muscle and parallel to the muscle's fibres having an inter-electrode distance of 20mm. Electrodes will be placed on muscles of the arm, neck, shoulder and back e.g. flexor carpi radialis muscles, biceps muscle, bilaterally from the trapezius muscles, and bilaterally from the erector spinae muscle. A wireless EMG system has been selected so that it is minimally invasive and does not impede the participants' movement with wires.

Data will be collected and analysed using EMG Works (Delsys Inc., Boston, MA, USA), with recommended normalisation, sampling, filtering and smoothing techniques. EMG recordings in previous data show significant changes during laparoscopic procedures in 70 - 85% of surgeons, mainly in neck, shoulders, hands, lower back, and lower extremities muscles. We will be obtaining recordings from muscles of the arm, neck, shoulder and back. Once the EMG signal has been normalise, basic EMG variables, such as frequency and amplitude, can provide information on how muscle fibre recruitment has changed, both at a single muscle as well across several muscles (activation / recruitment strategies), while a fatigue score can also be calculated. The normalisation process can afford the ability to compare between muscles as well as examine the muscles' activity different time points (i.e. within the same session or after a longer time has elapsed

[figure not shown]

Figure: Example wireless EMG sensor placement

Appendix 11

Electroencephalography (EEG) protocol

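### Appendix 6 measures two named confounders poorly: the activity boxes overlap at 60 minutes and stop at 150, and the 12-month symptom item cannot show current symptoms and omits the upper arm and elbow/forearm

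*Protocol*

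**What the plan says.** The protocol's account of Part 2 (Study Protocol) explains why Appendix 6 is completed on the test day. It covers, among other things, "physical fitness and presence of any musculoskeletal symptoms as these are potential confounding variables". The Study Design section likewise says that the questionnaire is there to account for potential confounders.

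Appendix 6 carries this out with two short blocks.

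- **Fitness.** A free-text item asks "What form of regular exercise do you undertake". A second item asks "How frequently do you undertake the above exercise in a week" and offers three boxes: "Inactive (less than 30minutes a week"), "Moderately Active (Between 30 and 60 minutes a week") and "Active (Between 60 and 150 minutes a week").
- **Symptoms.** One item asks "During the past 12 months have you had any trouble (ache/pain/discomfort/numbness) in any of the following please". It has Yes and No columns and nine rows: neck, right and left shoulder, right and left wrist, right and left upper back, right and left lower back.

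On EMG, the section on measurement of EMG and EEG places electrodes over the arms, neck, and upper and lower back. Appendix 10 says "Electrodes will be placed on muscles of the arm, neck, shoulder and back e.g. flexor carpi radialis muscles, biceps muscle", and adds trapezius and erector spinae on both sides. EMG is taken in 4 trainees from each of the four specialty-by-grade cells.

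**The concern.** A confounder can be described, stratified on or checked only as well as the form records it. Here the form is fixed in the protocol, so no later analysis plan can recover an answer that was never asked for.

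Objective 2 compares musculoskeletal fatigue between the specialties as a marker of competence. That reading is harder to defend if muscle activity in a trainee who is sore on the day cannot be told apart from activity that reflects less laparoscopic practice. The exclusion criteria do not mention musculoskeletal symptoms, so a trainee in discomfort may take part. In the text available, Appendix 6 is the only place where this would be noted.

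Fitness is the other confounder named in the same sentence. A scale with a shared boundary and no top category leaves the most active trainees to choose between an untrue answer and none.

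**Working it through.** The protocol gives no figure to reproduce here. The check sets the form beside its stated purpose and beside the EMG sites.

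**1. Activity boxes.** Let m be minutes of exercise a week.

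- Inactive: m < 30.
- Moderately active: 30 to 60.
- Active: 60 to 150.

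With end points included, m = 60 satisfies two boxes. With end points excluded, m = 30, 60 and 150 satisfy none. On either reading the boxes are not a clean partition. For any m above 150 the number of matching boxes is 0. The free-text item asks what kind of exercise is taken, so it does not ask for the missing amount.

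**2. Symptom window.** At any listed site there are three cases.

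- Trouble present on the test day: answer Yes.
- Trouble within the past 12 months, now resolved: answer Yes.
- No trouble within the past 12 months: answer No.

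So No rules out current trouble at that site, while Yes does not establish it. The form has 0 items on symptoms at the time of testing.

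**3. Symptom sites against EMG sites.**

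- Regions in Appendix 10 are arm, neck, shoulder and back. Three of the four (neck, shoulder, back) have a symptom row. The arm has only the adjacent wrist rows.
- Muscles named as examples: trapezius and erector spinae lie in listed regions (2 of 4). Flexor carpi radialis, in the forearm, has only the wrist beside it. Biceps has no row.

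**4. How much data is touched.**

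- Appendix 6 is for all Part 2 trainees: 20 + 20 = 40 planned.
- EMG subset: 4 cells x 4 trainees = 16. One trainee is 1/4 = 25% of a cell.
- EMG is recorded in round 2 of tasks 1 to 3 and throughout task 4: at most 5 + 3 + 3 + 15 = 26 minutes. Maximum task time over all rounds is 3 x 5 + 3 x 3 + 3 x 3 + 15 = 48 minutes, but that is not the EMG exposure.

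The protocol gives no figure for how many trainees exercise for more than 150 minutes a week, or how many would have arm symptoms or symptoms on the day.

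**The case against.** The strongest reply is that the form already does most of the job.

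- The past 12 months include the test day, so current pain at a listed site does appear as Yes, and trainees answering No form a usable symptom-free group at those sites. This stands. What is lost is the ability to split the Yes group.
- The protocol speaks of the presence of any symptoms, which need not mean only those felt on the day. This stands as a reason to keep the 12-month column; it is no reason to leave out a current one.
- Neck, shoulder and back are covered, the wrist rows lie next to the forearm, and the muscle list is illustrative. This stands, and it narrows the gap to the upper arm and the elbow/forearm. The main text still places electrodes over the arms, whichever muscles are chosen.
- A trainee above 150 minutes would probably tick the highest label, giving coarse data and not a blank. This is likely, but the form leaves it to the trainee, and the answer would be untrue as worded.
- With 16 trainees, adjustment could do little whatever the form asked. This also stands. The gain is in being able to identify an affected trainee for description or a sensitivity check.

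A reader might go further and infer that the fitness item also looks back 12 months, or that the study cannot account for its confounders at all. Neither is supported. The fitness item is weekly, and demographic details and laparoscopic experience have their own items. Nor do the documents show that the EMG comparison is biased: they give no prevalence of symptoms and no direction of effect.

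**Conclusion.** The point holds as a minor defect of measurement. The activity scale overlaps at 60 minutes on the natural reading and has no category above 150. The symptom item cannot separate resolved from current trouble, and it does not cover the upper arm or the elbow/forearm although EMG is recorded over the arms.

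The symptom gaps matter mainly for a secondary outcome in 16 trainees. The 25% figure says how much weight one trainee carries in a cell; it is not an estimate of bias. The activity boxes affect the fitness record of all 40 planned trainees, by an amount the documents do not let one state.

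Two assumptions apply. First, the activity table is complete as read: a row lost when the PDF was converted cannot be fully excluded, though nothing in the text suggests one. The overlap at 60 and the 12-month wording do not depend on this. Second, how these variables enter the analysis may be settled in an analysis plan that is not shown, and no criticism is made of that.

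**What to change.** Make three edits to Appendix 6.

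1. Replace the activity boxes with four exclusive ones: less than 30, 30 to less than 60, 60 to 150, and more than 150 minutes a week.
2. Keep the 12-month symptom column and add a 'today' column beside it.
3. Add rows for right and left upper arm and for right and left elbow/forearm.

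That is one more activity box, one more column and four more rows on a form already completed on the day. The cost is under a minute per trainee, with no change to recruitment, tasks or sample size. Which symptom column, if any, serves as a covariate for EMG is for the analysis plan. The expected use is to describe the EMG subset and to support a sensitivity check.
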